8.1.8 Multiple Comparisons/Multiplicity

In testing the secondary efficacy endpoints the overall Type I error will be controlled by requiring the two co-primary efficacy endpoints to be statistically significant. Specifically, failure of either one of the primary efficacy endpoints will invalidate the statistical significance of the secondary efficacy endpoints.

A stepwise process will be conducted for testing the secondary efficacy endpoints in order to control for multiplicity. These tests will be performed for only the ITT population. The testing process will terminate whenever a statistical test for a step is not significant. All subsequent tests for the remaining steps will be considered not significant. The order of testing is provided below.

Step Number	Secondary Endpoint
1	Percent change in inflammatory lesion count from Baseline to Week 12
2	Absolute change in inflammatory lesion count from Baseline to Week 8
3	Proportion of patients with the primary measure of success “Clear” (0) or “Almost clear” (1) in the IGA relative to Baseline at Week 8
4	Absolute change in inflammatory lesion count from Baseline to Week 4
5	Proportion of patients with the primary measure of success “Clear” (0) or “Almost clear” (1) in the IGA relative to Baseline at Week 4

In testing the supportive efficacy endpoints, the overall Type I error will be controlled by the Benjamini-Hochberg method. The Hochberg and Bejamini adaptive step-down Bonferoni method will be used within PROC MULTTEST in SAS (AHOLM option in PROC MULTTEST).

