#### 19.4.4. Supportive Efficacy Analyses

Appropriate descriptive statistics will be computed for all Supportive Efficacy parameters. Additionally, inferential testing for the following endpoints will use an ANOVA with factors of treatment, analysis center and the respective Baseline score. The overall Type I error will be controlled by the Benjamini-Hochberg method. Missing values will not be imputed.

- Mean change comparison in PAPSS item 1 (burning) between groups from Baseline to Week 12
- Mean change comparison in PAPSS item 2 (itching) between groups from Baseline to Week 12
- Mean change comparison in PAPSS item 3 (redness) between groups from Baseline to Week 12
- Mean change comparison in PAPSS item 4 (bumps) between groups from Baseline to Week 12

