8.7.4 Supportive Efficacy Analysis

Appropriate descriptive statistics will be computed for all supportive efficacy parameters.

In addition, the mean change comparison in PAPSS item 1 (burning), item 2 (itching), item 3 (redness) and item 4 (bumps) from Baseline to Week 12 will be analyzed using an analysis of variance (ANOVA) with factors of treatment, analysis center, and the respective Baseline score. Missing values will not be imputed.

A set of cumulative distribution function curves will be generated to allow for the evaluation of within-person change by treatment group. Specifically, 5 plots will be generated showing the change from Baseline to Week 12 (and/or other, earlier time points if so desired) by the cumulative percent of subjects for each of the treatment arms (change on the x-axis will be expressed as absolute change) on:

- PAPSS total scale scores

- The total scale score is the sum of PAPSS items 1 through 4.
 - PAPSS item 1 (burning) scores
 - PAPSS item 2 (itching) scores
 - PAPSS item 3 (redness) scores
 - PAPSS item 4 (bumps) scores

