Success	xx.x%	xx.x%	N/A	x.xxx ^d
Failure	xx.x%	xx.x%		

^a Least squares means, standard deviations and treatment p-value from an analysis of covariance with factors of treatment and analysis center and the Baseline lesion count as a covariate. Negative least squares means values represent decrease from Baseline.

^b Skewness test, based on methods presented by J.H. Zar (1984), assessed for each imputed dataset. The average p-value is presented.

^c P-value from a ranked analysis of covariance with factors of treatment and analysis center and the Baseline lesion count as a covariate.

^d P-value from a logistic regression with factors of treatment group and analysis center.

Note: Multiple imputation (MCMC) used to impute missing values.

SOURCE: USERNAME\SPONSOR\PROJECT\JOBNAME (DATE, TIME)

Table 14.2.6.1: Secondary Efficacy Analyses
(Intent-to-Treat Population)
(Page 3 of 3)

	E-BPO 5% Cream (N=xxx)	Vehicle Cream (N=xxx)	Skewness P-Value	Treatment P-Value
Inflammatory Lesion Count – Absolute Change from Baseline to Week 4				
LSMean ^a	xx.x	xx.x	x.xxx ^b	x.xxx ^a
LSSD ^a	xx.xx	xx.xx		x.xxx ^c
Achieving Clear or Almost Clear at Week 4				
Success	xx.x%	xx.x%	N/A	x.xxx ^d
Failure	xx.x%	xx.x%		

^a Least squares means, standard deviations and treatment p-value from an analysis of covariance with factors of treatment and analysis center and the Baseline lesion count as a covariate. Negative least squares means values represent decrease from Baseline.

^b Skewness test, based on methods presented by J.H. Zar (1984), assessed for each imputed dataset. The average p-value is presented.

^c P-value from a ranked analysis of covariance with factors of treatment and analysis center and the Baseline lesion count as a covariate.

^d P-value from a logistic regression with factors of treatment group and analysis center.

Note: Multiple imputation (MCMC) used to impute missing values.

SOURCE: USERNAME\SPONSOR\PROJECT\JOBNAME (DATE, TIME)

Table 14.2.7.1: Patient Assessment of Papulopustular rosacea Signs and Symptoms (PAPSS) Analyses at Week 12
(Intent-to-Treat Population)

	E-BPO 5% Cream (N=xxx)	Vehicle Cream (N=xxx)	Treatment P-Value
PAPSS Total Scale Score – Absolute Change from Baseline to Week 12			
LSMean ^a	xx.x	xx.x	x.xxx ^a
LSSD ^a	xx.xx	xx.xx	
PAPSS Burning – Absolute Change from Baseline to Week 12			
LSMean ^a	xx.x	xx.x	x.xxx ^a
LSSD ^a	xx.xx	xx.xx	
PAPSS Itching – Absolute Change from Baseline to Week 12			
LSMean ^a	xx.x	xx.x	x.xxx ^a

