LSSD ^a	xx.xx	xx.xx	
PAPSS Redness – Absolute Change from Baseline to Week 12			
LSMean ^a	xx.x	xx.x	x.xxx ^a
LSSD ^a	xx.xx	xx.xx	
PAPSS Bumps – Absolute Change from Baseline to Week 12			
LSMean ^a	xx.x	xx.x	x.xxx ^a
LSSD ^a	xx.xx	xx.xx	

^a Least squares means, standard deviations and treatment p-value from an analysis of variance with factors of treatment, analysis center, and the respective Baseline score. Negative least squares means values represent decrease from Baseline.

Note: No imputation of missing values. To control family-wise type I error rate at 5%, the Benjamini-Hochberg procedure (Hochberg and Bejamini adaptive step-down Bonferroni method) was utilized, and each p-value with an (*) is to be considered statistically significant.

SOURCE: USERNAME\SPONSOR\PROJECT\JOBNAME (DATE, TIME)

Table 14.2.8.1: Summary of Patient Assessment of Papulopustular Rosacea Signs and Symptoms (PAPSS) at Each Evaluation
(Intent-to-Treat Population)
(Page 1 of 15)

Total Scale Scores	E-BPO 5% Cream (N=xxx)	Vehicle Cream (N=xxx)
Baseline		
n	xx	xx
Mean	xx.x	xx.x
SD	xx.xx	xx.xx
Median	xx.x	xx.x
Min. to Max.	xx to xx	xx to xx
Week 2		
n	xx	xx
Mean	xx.x	xx.x
SD	xx.xx	xx.xx
Median	xx.x	xx.x
Min. to Max.	xx to xx	xx to xx
Change from Baseline		
n	xx	xx
Mean	xx.x	xx.x
SD	xx.xx	xx.xx
Median	xx.x	xx.x
Min. to Max.	xx to xx	xx to xx

Note: No imputation of missing values.

Total scale score is the sum of all PAPSS items.

SOURCE: USERNAME/SPONSOR/PROJECTJOBNAME (DATE,TIME)

Table 14.2.8.1: Summary of Patient Assessment of Papulopustular Rosacea Signs and Symptoms (PAPSS) at Each Evaluation
(Intent-to-Treat Population)
(Page 2 of 15)

Total Scale Scores	E-BPO 5% Cream (N=xxx)	Vehicle Cream (N=xxx)
Week 4		
n	xx	xx
Mean	xx.x	xx.x
SD	xx.xx	xx.xx
Median	xx.x	xx.x
Min. to Max.	xx to xx	xx to xx
Change from Baseline		
n	xx	xx
Mean	xx.x	xx.x
SD	xx.xx	xx.xx
Median	xx.x	xx.x
Min. to Max.	xx to xx	xx to xx
Week 8		
n	xx	xx
Mean	xx.x	xx.x
SD	xx.xx	xx.xx
Median	xx.x	xx.x
Min. to Max.	xx to xx	xx to xx
Change from Baseline		
n	xx	xx
Mean	xx.x	xx.x
SD	xx.xx	xx.xx
Median	xx.x	xx.x
Min. to Max.	xx to xx	xx to xx

Note: No imputation of missing values.

Total scale score is the sum of all PAPSS items.

SOURCE: USERNAME\SPONSOR\PROJECT\JOBNAME (DATE,TIME)

Table 14.2.8.1: Summary of Patient Assessment of Papulopustular Rosacea Signs and Symptoms (PAPSS) at Each Evaluation
(Intent-to-Treat Population)
(Page 3 of 15)

Total Scale Scores	E-BPO 5% Cream (N=xxx)	Vehicle Cream (N=xxx)

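### Supportive PAPSS tests: the SAP instructs an adaptive Holm procedure, labels it Benjamini-Hochberg and claims 5% family-wise control; the test family and the total score are also inconsistent (minor)

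*SAP*

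**What the plan says.** Protocol 19.4.4 lists four inferential supportive tests, the change from Baseline to Week 12 in each PAPSS item, and says "The overall Type I error will be controlled by the Benjamini-Hochberg method". It does not mention AHOLM.

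SAP 8.1.8 repeats the name ("In testing the supportive efficacy endpoints, the overall Type I error will be controlled by the Benjamini-Hochberg method") and then gives the programming instruction: "adaptive step-down Bonferoni method will be used within PROC MULTTEST in SAS (AHOLM option in PROC MULTTEST".

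The note to Table 14.2.7.1 joins the two: "To control family-wise type I error rate at 5%, the Benjamini-Hochberg procedure (Hochberg and Bejamini adaptive step-down Bonferroni method) was utilized". It adds that "each p-value with an (*) is to be considered statistically significant".

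On the family, SAP 8.7.4 plans tests for "the mean change comparison in PAPSS item 1 (burning), item 2 (itching), item 3 (redness) and item 4 (bumps) from Baseline to Week 12", which is four. Table 14.2.7.1 opens with a fifth row carrying its own treatment p-value, "PAPSS Total Scale Score – Absolute Change from Baseline to Week 12", under the same multiplicity note.

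On the total, SAP 8.7.4 says "The total scale score is the sum of PAPSS items 1 through 4". Protocol 14.5 instead averages items 1, 2 and 4, leaving redness out, and intends that score for efficacy hypotheses. SAP section 2 gives the SAP precedence over the protocol. SAP section 10, which lists changes as small as a dropped subgroup, does not mention the new total.

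**The concern.** Benjamini-Hochberg is a step-up procedure that controls the false discovery rate. AHOLM is a step-down procedure whose thresholds depend on an estimate of the number of true null hypotheses (m0). They are not two names for one method, and a 5% family-wise statement does not carry from one to the other. The asterisk in Table 14.2.7.1 declares patient-reported results significant, so the error rate printed beneath it should be true of what was run.

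The family definition decides whether the total score can earn an asterisk at all. The total's definition decides what that asterisk would mean, because redness is in one version and out of the other.

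**Working it through.** **Inputs.** From the documents: two-sided 0.05 (SAP 8.1); m = 4 tests (SAP 8.7.4) or m = 5 (Table 14.2.7.1). Not in the documents, so assumed and varied: number of responding items, size of their effects, correlation between items, and the m0 estimator.

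**1. The stated 5%.** If no item responds and tests are independent, Benjamini-Hochberg does give 5% (simulated 0.0500 for m = 4, 0.0497 for m = 5). The question is what happens when some items respond and others do not.

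**2. Benjamini-Hochberg, worst independent case.** Its thresholds are 0.05 × i/m.
- m = 4, two items certain to be rejected, two null. A false mark occurs if the smaller null p-value is ≤ 0.0375 or both are ≤ 0.05: 1 − (1 − 0.0375)² + (0.05 − 0.0375)² = 0.07359 + 0.00016 = **0.0737**.
- m = 5, two certain, three null, thresholds 0.03, 0.04, 0.05 for the ordered null p-values. The probability of no false mark starts from all three above 0.03. Subtract at least two in (0.03, 0.04], then all three ≤ 0.05 with at most one in (0.03, 0.04]: 0.97³ − [3 × 0.01² × 0.96 + 0.01³] − 4 × 0.01³ = 0.912673 − 0.000289 − 0.000004 = 0.91238. The error is **0.0876**.
- Plain Holm in the first setting: 1 − (1 − 0.05/2)² = 0.0494.

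**3. Benjamini-Hochberg, correlated items.** Simulation with m = 4, z = 3 for responding items, correlation 0.3 to 0.7:

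| Responding items | Family-wise error |
|---|---|
| 1 | 4.8-6.2% |
| 2 | 4.7-6.1% |
| 3 | 3.4-4.2% |

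**4. AHOLM, the procedure instructed.** Thresholds are 0.05/min(m0, m − i + 1). The documents do not give the m0 estimator. Assumed rule: slopes (1 − p(i))/(m + 1 − i), stop at the first decrease (else the last), m0 = 1/slope + 1, capped at m. Maxima over 0 to m − 1 responding items, shifts 3, 5 and 20, correlation 0 to 0.7:
- m0 rounded up: about 5.1% (m = 4) and 5.2% (m = 5);
- m0 rounded down: about 6.0% (m = 4) and 6.6-6.7% (m = 5).

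The standard error at 200,000 runs is √(0.05 × 0.95/200,000) = 0.05 percentage points. Holm's simulated maximum on the same grid was 5.07%, so the rounded-up excess for four tests cannot be told from simulation noise.

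**5. Are the procedures interchangeable?** Take p = 0.008, 0.015, 0.028, 0.045, 0.30. Benjamini-Hochberg (0.01, 0.02, 0.03, 0.04, 0.05) marks 3. The adaptive step-down marks 1, 1, 2, 2 or 4 for m0 = 5, 4, 3, 2, 1. No whole-number m0 gives 3, so the bracketed equation in the table note is false.

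**6. Family size.** With all items responding (mean z 2 to 3, correlation 0.3 to 0.7), going from four to five tests changes the marking of the four items in under 1% of simulated trials under AHOLM, with the assumed m0 rules.

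**7. The total.** Mean versus sum is only a rescaling; adding redness is what matters. With equal SDs, correlation ρ, and a redness effect e times that of the other items, the standardised effect of the SAP total relative to the protocol total is [(3 + e)/√(4 + 12ρ)] / [3/√(3 + 6ρ)]. The last column starts from z = 2.5 (p = 0.012) on the protocol total.

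| e | ρ = 0.3 | ρ = 0.5 | ρ = 0.7 | p on SAP total |
|---|---|---|---|---|
| 0 | 0.795 | 0.775 | 0.762 | 0.047-0.057 |
| 1 | 1.060 | 1.033 | 1.016 | 0.008-0.011 |
| 2 | 1.325 | 1.291 | 1.270 | 0.0009-0.0015 |

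**The case against.** The best reply is that execution is not in doubt. SAP 8.1.8 names a software option, the table note repeats the same method in brackets, and the SAP overrides the protocol's bare reference to Benjamini-Hochberg. This stands. A reader might infer that the programmer must choose between two procedures, or that the supportive tests will run at 7-9% family-wise error. The documents support neither. The choice is made, and those rates belong to the procedure that is named but not run. They also need independence and near-certain rejections, whereas the PAPSS items come from the same patients.

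A second reply is that the m0 estimator is fixed by reference to the software, so its absence from the SAP is not a gap in method. This stands in part. The procedure is specified, but the printed 5% claim still cannot be checked from the plan, and a reader should not infer that AHOLM has been shown to fail. The 6.0-6.7% rests on an assumed rounding.

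Third, SAP 8.7.4 uses the total only for the cumulative distribution plots, and the SAP's sum is explicit and governs. That settles which total is computed. It explains neither the total's p-value in Table 14.2.7.1 nor the silence of section 10.

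**Conclusion.** The plan is wrong as written, for the supportive PAPSS tests only. The instructed method carries the wrong name, and the 5% family-wise statement is not true in general of the method named. For AHOLM, 5% is approximately met or modestly exceeded, depending on an estimator the documents do not give.

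The four-versus-five conflict lies within the SAP, so the precedence rule cannot resolve it. Its consequence is whether the total can be marked; the effect on the items is slight. The total's change is an undeclared departure from the protocol that can move its p-value either way, or hardly at all if redness responds like the other items.

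The worst-case Benjamini-Hochberg rates follow from its thresholds. The other simulated figures rest on the assumed correlations, effects and m0 rules. A reader might infer that the trial's main error control is compromised, but it is not: the co-primary requirement and the fixed-order secondary tests in SAP 8.1.8 do not use this procedure. Severity is minor.

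**What to change.** In SAP 8.1.8 and the Table 14.2.7.1 note, name one procedure and claim only the error rate it delivers:
- Holm, if the 5% family-wise statement is to stay, since it needs no m0 estimate; or
- AHOLM, without the Benjamini-Hochberg label, with its m0 estimator stated and without claiming exact 5% control unless that is shown; or
- Benjamini-Hochberg, claiming false discovery rate control only.

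State the same family in 8.7.4 and the table: either four items with the total outside the marking, or five tests. Use the Protocol 14.5 total, or declare and justify the four-item sum in section 10. Settle this before the blind is broken.

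The cost is a few lines of SAP wording, at most one PROC MULTTEST option, one line in the table shell and one entry in section 10. The downside is that fewer supportive items may be marked, chiefly under Holm.

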8. STATISTICAL AND ANALYTICAL PLANS

8.1 General Methodology

All statistical processing will be performed using SAS® version 9.3 or later unless otherwise stated. Statistical significance will be based on two-tailed tests of the null hypothesis resulting in p-values of 0.05 or less. These methods are intended to analyze the results of the study.

The primary method of handling missing efficacy data will be based on estimation using the method of Markov Chain Monte Carlo (MCMC) imputation. This method provides robust estimation when the pattern of missingness is arbitrary. Additionally, the estimation will be done for each treatment group separately so that the pattern of missingness for one group does not influence the estimation of missing data for another group. Groups of complete datasets following the estimation will be concatenated to form analysis datasets for the comparative analyses and subsequent imputation result inference with SAS PROC MIANALYZE.

Descriptive statistics will also be derived from the multiply imputed datasets.

Additionally, a model-based multiple imputation process will be used as a sensitivity analysis to the MCMC imputation. Finally, the absolute change in lesion count will be analyzed using a repeated measures analysis of covariance (ANCOVA) for lesion count data and a repeated measures logistic regression model (generalized estimating equations) for the dichotomized IGA.

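### PAPSS p-values can be starred as significant even when a co-primary fails, because the PAPSS family has its own 5% and no gate

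*SAP*

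**What the plan says.** SAP 8.1 sets the general rule: "Statistical significance will be based on two-tailed tests of the null hypothesis resulting in p-values of 0.05 or less".

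SAP 8.1.8 then builds a hierarchy for the secondary endpoints. Both co-primaries must be significant, and "failure of either one of the primary efficacy endpoints will invalidate the statistical significance of the secondary efficacy endpoints". Five secondary steps follow in fixed order: "The testing process will terminate whenever a statistical test for a step is not significant". Protocol 19.4.3 has the same rule.

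The supportive endpoints get a separate paragraph at the end of SAP 8.1.8: "In testing the supportive efficacy endpoints, the overall Type I error will be controlled by the Benjamini-Hochberg method". The next sentence names a different procedure for the same family, the adaptive Holm method (the AHOLM option of PROC MULTTEST). Protocol 19.4.4 says: "The overall Type I error will be controlled by the Benjamini-Hochberg method". The inferential tests concerned are the four PAPSS items at Week 12 (protocol 19.4.4, SAP 8.7.4). The shell of SAP Table 14.2.7.1 adds a p-value for the total score, so the family has four or five tests.

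The note to that table states the level, "To control family-wise type I error rate at 5%, the Benjamini-Hochberg procedure", and how a result is declared: "each p-value with an (*) is to be considered statistically significant". None of these places mentions the co-primaries or the secondary sequence.

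**The concern.** The co-primary and secondary chain already uses the full two-sided 0.05. The PAPSS family starts again at 5% whatever happened above it. A trial could miss a co-primary, forfeit all five secondary claims under its own rule, and still star burning, itching, redness or bumps as statistically significant, next to wording that says the overall Type I error is controlled. Endpoints ranked below the secondaries would then be open to a declaration of significance that the secondaries are denied.

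This does not depend on which adjustment is used inside the PAPSS family. What is missing is the link between families.

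**Working it through.** **1. Is there a link anywhere?** The gate in SAP 8.1.8 and protocol 19.4.3 names only the secondary endpoints. SAP 8.1.8 (supportive paragraph), SAP 8.7.4, protocol 19.4.4 and the Table 14.2.7.1 note describe the PAPSS tests, and none sets a condition. No other section restores one. The structural point needs no simulation.

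**2. The plan's own figure: 5% within the PAPSS table.** With four null items and independent tests:
- Benjamini-Hochberg: 5.0%.
- Holm: 1 − (1 − 0.05/4)^4 = 1 − 0.9875^4 = 4.9%.

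The stated 5% is thus reproduced under these conditions. Simulation of correlated two-sided z-tests (400,000 draws; four items, or five with the total score) gives 3.0% to 4.9% with Holm, 3.7% to 5.0% with Benjamini-Hochberg, and 5.4% to 6.2% with adaptive Holm. The adaptive version is modelled with a lowest-slope estimate of the number of true nulls, which is an assumption. If two of the four items have strong real effects, Benjamini-Hochberg gives 6.9% to 7.4% on the other two.

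**3. Across families, one null above PAPSS.** Take one co-primary truly effective, the other null, and all PAPSS items null. The null co-primary is then tested at a full 0.05.
- Independent tests: 1 − (1 − 0.05)(1 − 0.05) = 9.75%.
- Additive bound for two 5% families: 0.05 + 0.05 = 10%.
- One common correlation among all tests (500,000 draws, four items):

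| Correlation (assumed) | Holm | Benjamini-Hochberg |
|---|---|---|
| 0 | 9.7% | 9.8% |
| 0.5 | 8.3% | 8.5% |
| 0.8 | 6.4% | 6.7% |

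- Separate correlations (PAPSS items 0 to 0.7, PAPSS with primaries 0 to 0.6, between primaries 0 to 0.9): 7.0% to 9.8% with Holm or Benjamini-Hochberg, and 9.3% to 10.4% with adaptive Holm.

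Five points of each figure are the null co-primary's own error, which exists with or without PAPSS. With Holm, the missing gate adds 9.7 − 5 = 4.7, 8.3 − 5 = 3.3 and 6.4 − 5 = 1.4 points at correlations 0, 0.5 and 0.8. The same argument applies to a null secondary reached after true effects ahead of it.

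Ten per cent is not a strict ceiling. With Benjamini-Hochberg and two of four PAPSS items truly effective, the simulated figure is 11.2% to 12.0%.

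**4. Across families, global null.** Both co-primaries must be falsely significant before the upper chain makes any claim. With independent tests that chance is 0.05 × 0.05 = 0.0025, so the total is 1 − (1 − 0.0025)(1 − 0.05) = 5.24%. Simulated: 4.3% to 6.1% with Holm or Benjamini-Hochberg, and 5.6% to 7.9% with adaptive Holm.

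**5. With PAPSS gated behind both co-primaries.**
- One co-primary null: 5.0% to 5.1%.
- Global null: 0.25% to 0.9%.
- All primary and secondary effects real, PAPSS null: 4.3% to 4.9% with Holm, 5.5% to 5.9% with adaptive Holm.

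Errors are counted in both directions. Counting only results that favour active would roughly halve the per-test rates.

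**The case against.** The strongest defence is that the plan never promises 5% across all families. SAP 8.1.8 limits its sentence to the supportive endpoints, the 5% stands in the note to the PAPSS table, and no section gives a numeric rate for the whole trial. The endpoints are labelled supportive, no PAPSS labelling claim is planned, and a separately adjusted supportive family is a recognisable design choice. The co-primary conclusions are untouched.

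Much of this stands. A reader might infer that the trial's overall Type I error simply is 8% to 10% instead of a promised 5%. The documents do not support that. Those figures need one null hypothesis tested at a full 5% behind truly effective ones, null PAPSS items, and low to moderate correlation. Under the global null the excess is small. The only numeric 5% belongs to the PAPSS table.

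What does not fall away is the wording and the asterisk. Both documents use the word *overall*, the SAP plans a declaration of significance with no condition, and protocol 14.5 intends the PAPSS total score for testing efficacy hypotheses. A supportive label alone does not tell the reader of the table that a starred result is nominal when the trial has failed.

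It is also fair to object that requiring all five secondary steps first would be stricter than needed to stop PAPSS claims in a failed trial. The documents give no power for the Week 4 steps, so the cost of that stricter gate cannot be judged from them.

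**Conclusion.** The point holds in a limited form. PAPSS p-values can be starred as statistically significant after a co-primary has failed, and error is controlled at most within the PAPSS family. Across families the chance of any false claim can reach about 10% in the configuration of step 3, and is near 5% under the global null with Holm or Benjamini-Hochberg. The correlations, and the form of the adaptive method, are assumptions. The absence of a gate is read directly from the text and rests on neither.

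This should be settled before unblinding because it changes what may be declared significant. It does not threaten the primary analysis.

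Naming both Benjamini-Hochberg and adaptive Holm for one family is a separate inconsistency. It bears on this point because a gate alone does not give exactly 5% with the adaptive method as modelled.

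**What to change.** Before unblinding, choose one of two changes.

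**(a) Nominal.** Label all PAPSS p-values nominal and remove the asterisk. Delete the error-control sentence for this family in SAP 8.1.8 and in protocol 19.4.4, and the family-wise 5% statement in the Table 14.2.7.1 note. The cost is any formal PAPSS claim.

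**(b) Gate.** State in SAP 8.1.8 and the table note that the PAPSS tests are inferential only if both co-primaries are significant, and that otherwise the p-values are nominal and carry no asterisk. Replace *overall* with *within the PAPSS family* in SAP 8.1.8 and protocol 19.4.4. The cost is no formal PAPSS claim if a co-primary fails. A null secondary reached after both co-primaries succeed would still add up to 5 points.

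If full control across families is wanted, PAPSS must also follow the secondary sequence, at the cost of no formal PAPSS claim whenever that sequence stops early.

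Either change takes a few sentences and one table note, recorded in SAP section 10. All p-values can still be shown. Under (b), the SAP must also name a single procedure for the family and say whether it covers four tests or five.
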